## BACKGROUND

Shortness of breath is a frequent symptom and can be caused by many different disorders from several different organs. Many patients experience shortness of breath as a result of heart or lung disease or as a complication of thoracic surgery. Shortness of breath is a subjective sensation and can be caused by a lack of oxygen, reduced ventilation or dysfunctional breathing muscles.

The diaphragm is the main breathing muscle. Decreased ability to contract the diaphragm causes shortness of breath. The investigation of dysfunction of the diaphragm is complicated by the fact that newly discovered shortness of breath is not specific to diaphragm dysfunction and can be caused by the many other causes of shortness of breath. Diaphragm dysfunction is therefore an overlooked cause of shortness of breath.

We want to shed more light on the function of the diaphragm. Therefore, we will do two studies. The first is a method study in which different ultrasound methods are compared with the golden standard, x-ray transillumination, in healthy, heart- and lung-diseased patients. The second study will assess the diaphragm function in patients after thoracic surgery (lung surgery and heart transplantation) and in patients where severe heart failure necessitates the need for a mechanical heart heart (Left Ventricular Assist Device, LVAD).

## STUDY 1:

It is difficult to measure the function of the diaphragm. There are various examination methods to assess the function of the diaphragm. Imaging studies, such as x-rays (fluoroscopy) and ultrasound examinations, are used. X-ray examination of the chest and diaphragm during breathing is considered an older gold standard, but is not really used much in everyday clinical practice. Ultrasound has gradually become the common examination method, as ultrasound examination allows a number of advantages such as easier use, less set up and avoidance of radiation risk. There are several different methods for ultrasound determination of diaphragm function, none are sufficiently validated and there is no consensus about the optimal method. There is a need for a comparison of different methods with transillumination (golden standard) to establish a precise basis for comparison. [1]

## STUDY 2:

The etiology of shortness of breath is multifactorial, and shortness of breath can be a symptom of a wide range of lung or heart diseases. In failing heart pump function, shortness of breath is one of the most frequent symptoms. Heart failure can be treated with various types of medicine, but in severe heart failure so that sufficient circulation cannot be maintained, heart transplantation may be the only treatment. Shortage of transplant organs results in waiting time for transplantation. Therefore, an LVAD has been developed that can maintain adequate blood circulation as either temporary treatment before heart transplantation or as definitive treatment in patients who cannot undergo regular heart transplantation. The LVAD is implanted in the thorax and helps pump blood from the left ventricle into the aorta. The LVAD is located on top of the left hemidiaphragm and can therefore inhibit the movement of the diaphragm. Thereby, the LVAD can give rise to shortness of breath, and in patients who have concurrent heart failure, it can thus be difficult to assess whether shortness of breath is due to heart failure or reduced diaphragm function. Treatment that these conditions are different.

Heart transplantation entails a complete replacement of the heart. Due to the close relationship with the phrenic nerve, this can be damaged during the operation and thus result in reduced diaphragm function.

Some diseases, e.g. Cancer of the lung, mediastinum and esophagus requires thoracic surgery. Nerves to the diaphragm can be damaged during the operation and thereby cause reduced diaphragm function, which can lead to shortness of breath. Pleural effusion is common after thoracic surgery and also manifests as shortness of breath. In addition, patients often have other competing diseases such as chronic obstructive pulmonary

disease (COPD) or heart failure, which can also cause shortness of breath. This results in complex diagnostic conditions and complicates the investigation of shortness of breath after thoracic surgery.

## HYPOTHESIS/AIM

- 1. To compare the precision of different ultrasound examination methods for assessing diaphragm function compared with X-ray translucency.
- 2. Investigate whether LVAD implantation, heart transplantation and thoracic surgery affect diaphragm function.

## TITLES

- 1. Precision of sonographic measures of diaphragm function.
- 2. The role of diaphragm mobility in heart failure requiring LVAD, heart transplant and thoracic surgery.

## METHOD

#### DESIGN

#### STUDY 1:

Methodology study. Different ultrasound methods for evaluating diaphragm function are compared with transillumination of the diaphragm.

#### STUDY 2:

Prospective, observational study of diaphragm function before and after thoracic surgery types that may affect diaphragm function.

## SETTING

All studies are carried out at Aarhus University Hospital as a collaboration between Heart Diseases, Lung Diseases, Cardiopulmonary and Vascular Surgery, Anesthesia and Surgery and Intensive Care.

#### PARTICIPANTS

## STUDY 1:

Participants are divided into 3 categories: 1/3 healthy, 1/3 lung medicine patients and 1/3 patients who have had a heart transplant or LVAD implanted. Everyone over 50 years.

#### STUDY 2:

Patients who must undergo lung surgery or surgery for oesophageal cancer with interventions in the chest cavity at Cardiopulmonary and Vascular Surgery as well as patients with severe heart failure who must undergo heart transplantation or LVAD and/or are scheduled for this.

## STUDY 1:

Inclusion criteria:

- o Completed informed consent
- 1 of the following:
  - Quick control person
  - Disease in the lungs: COPD or Idiopathic Pulmonary Fibrosis.
  - Disease of the heart that has led to a heart transplant or LVAD

#### Exclusion criteria:

- Known diaphragm dysfunction
- o Neuromuscular disease
- Pleural effusion. Discovered during the investigation
- o Pneumothorax. Discovered during the investigation
- Healthy group only (1/3): Significant comorbidity affecting heart or lung function (hypertension and mild valvular disease without symptoms is ok), including diagnosed COPD.
- Only healthy group (1/3) and lung disease group (1/3): Previous operation in the thorax

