## STRENGTH CALCULATION

## STUDY 1:

There is no data available for test-retest variance within ultrasound methods or fluoroscopy. It is therefore not possible to make a power calculation of how the spread in the comparison of two methods will be (Limits of agreement with Bland-Altman analysis). The starting point is therefore the bias (absolute difference in mean value) between an ultrasound method (m-mode method) and transillumination. As this is a methodological study, greater requirements are set than in study 2 (see below) for which bias can be detected. Assuming equal variation for the two methods, a detection of bias of 10% (SD 36%, own data for M-mode method) will require 92 participants (power 0.8 and alpha 0.05). Due to uncertainty about SD on the screening method, it is desired to include 100 participants.

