## SUMMARY OF DESIRED NUMBER OF INCLUDED PATIENTS

## STUDY 1:

We want 100 patients (34 healthy, 33 pulmonary medicine patients and 33 patients who have had a heart transplant/LVAD) included, distributed equally between the 3 groups to compensate for drop-outs and increase power.

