## ETHICAL CONSIDERATIONS

## STUDY 1:

Ultrasound examinations and lung function examination are without any kind of risks or discomfort for the participants and the examinations do not contain any ethical considerations.

The participants will be X-rayed. The radiation dose is minimal and the expected, accumulated dose of 0.1-1mSievert must be compared to being exposed to approx. 3 mSv for background radiation annually. The expected radiation dose corresponds to an increased risk of serious cancer of 1 in 100,000. If it turns out that there is good correlation and agreement between ultrasound methods and fluoroscopy, there will be no need for fluoroscopy in the future if dysfunction of the diaphragm muscle is suspected, and future patients will therefore be spared radiation. [6] It will also be possible to reduce the radiation dose employees are exposed to. In study 1, only subjects aged  $\geq$ 50 years are included in order to minimize the risk of developing cancer secondary to the experiment. There have been no studies in which the radiation dose during fluoroscopy is indicated, as it depends on the apparatus and method. In this study, we record the total radiation dose, and the total radiation dose is closely monitored.

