## PERSPECTIVE

#### STUDY 1:

The first study will identify the optimal research method. This makes it much easier and safer to examine future patients, as you want to avoid X-rays.

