## Exclusion criteria:

- o Known dysfunction of the diaphragm
- Chronic nerve or muscle disease
- Fluid in the lung cavity. Discovered during the investigation
- Air in the lung cavity. Discovered during the investigation
- Only group healthy (1/3): Significant disease affecting heart or lung function (high blood pressure and mild heart valve disease without symptoms is ok), including diagnosed smoker's lungs.
- $\circ$  Only healthy group (1/3) and lung disease group:

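### Study 1 excludes known diaphragm dysfunction in all three groups, although a good result is to end the need for fluoroscopy when dysfunction is suspected, so agreement at low movement may be poorly tested

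*Combined protocol and SAP*

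**What the plan says.** All references are to the combined protocol and SAP.

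- **Who is kept out.** The Study 1 exclusion list contains "Known diaphragm dysfunction" with no group attached. The layman's summary repeats it as "Known dysfunction of the diaphragm". "Neuromuscular disease" is also excluded in every group. Other items in the list are tied to groups, for example "Only healthy group (1/3) and lung disease group (1/3): Previous operation in the thorax".
- **Who is enrolled.** "We want 100 patients (34 healthy, 33 pulmonary medicine patients and 33 patients who have had a heart transplant/LVAD) included" (Summary of desired number of included patients). The lung group has COPD or idiopathic pulmonary fibrosis.
- **What the result is for.** Ethical considerations, Study 1, says that with good correlation and agreement "there will be no need for fluoroscopy in the future if dysfunction of the diaphragm muscle is suspected". The layman's summary makes the same statement on good correlation alone.
- **How agreement is assessed.** Fluoroscopy and ultrasound are recorded simultaneously. Data analysis, Study 1, plans a paired test of each method against fluoroscopy, a Bland-Altman plot and a correlation, all on the pooled sample. The primary endpoint is M-mode movement of the right hemidiaphragm.

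**The concern.** A comparison of two measurement methods supports conclusions over the range in which both were observed. The stated use concerns patients who may have weak or absent diaphragm movement, and the design removes those in whom this is already recognised. If ultrasound and fluoroscopy agree well at normal excursion but diverge at low excursion, a pooled analysis dominated by preserved movement could still look good. Fluoroscopy might then be abandoned in the patients for whom agreement was least examined.

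The exclusion has an obvious purpose in Study 2, where it protects the baseline of a before/after comparison. In Study 1 each participant is measured by both methods at the same time, so dysfunction does not bias the paired difference. It supplies the low end of the range. The protocol gives no reason for applying the exclusion to the diseased groups.

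**Working it through.** **1. The passages side by side.**

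| Question | What the documents give |
|---|---|
| Is the exclusion limited to the healthy group? | No. Neighbouring items are limited by group; this one is not. |
| Can low-movement participants still enter? | Yes, if unrecognised or only suspected. The Background calls dysfunction overlooked, and its Study 2 part says transplantation can injure the phrenic nerve and an LVAD can restrict the diaphragm. |
| Does the LVAD effect reach the primary endpoint? | Not evidently. The Background places the device on the left hemidiaphragm; the primary endpoint is the right. |
| Is a minimum number with low movement set? | No. |
| Is dysfunction or low movement defined? | No. |
| Is agreement analysed by size of movement? | Only as far as a reader can see it in the Bland-Altman plot. No separate bias or limits are planned. |
| Is the replacement statement limited to those enrolled? | No. |

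**2. The plan's own sample size.** Strength calculation, Study 1, states that "a detection of bias of 10% (SD 36%, own data for M-mode method) will require 92 participants (power 0.8 and alpha 0.05". The paired two-sided formula gives n = ((1.960 + 0.842) × 36 / 10)² = 101.7, so 102 (104 with the t distribution). The stated 92 is not reproduced on that reading. That is a separate matter and nothing here depends on it. What matters here is that the calculation addresses mean bias in the whole sample. It sets no precision for limits of agreement, overall or at low movement.

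**3. Why the 36% cannot size this effect.** The Study 2 calculation gives M-mode movement of 6.65 mm (SD 2.38), and 2.38 / 6.65 = 35.8%. The 36% therefore looks like the spread of M-mode values between people, not the SD of paired differences. The protocol says it has no test-retest variance for either method. A confidence interval for bias among low-movement participants built on 36% would be unsupported. Normal-tail counts from 6.65 and 2.38 do not help either: they come out the same whether or not the exclusion is applied.

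**4. An illustration in units of the unknown SD of differences.** The documents give no rate of undiagnosed dysfunction, so the rates below are assumptions. They apply to the 33 + 33 = 66 diseased participants. The approximate 95% half-width for a limit of agreement, in SD units, is t(0.975, n−1) × √(1/n + 1.96² / (2(n−1))).

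| Assumed rate | Expected number of 66 | Half-width (SD units) |
|---|---|---|
| 5% | about 3 | 4.9 |
| 10% | about 7 | 1.7 |
| 20% | about 13 | 1.1 |
| 30% | about 20 | 0.8 |
| all 100 participants | – | 0.34 |

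At assumed rates of 5% to 20%, separate limits for such participants would be about 3 (1.06 / 0.34) to 14 (4.89 / 0.34) times less precise than for the whole sample. This shows how precision depends on a number the plan leaves open. It does not measure what the exclusion removes. It also treats the low-movement participants as a stand-alone subgroup; limits modelled across the whole range would use more of the data.

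**The case against.** The strongest reply is that known is not the same as suspected. Only recognised cases are excluded, the protocol itself calls dysfunction overlooked and says fluoroscopy is little used in practice, and two thirds of the sample have heart or lung disease. Recognised cases may be few. This stands. A reader might infer that agreement at low movement goes untested, or that patients with dysfunction cannot enter; the documents support neither. What remains is that their number is neither planned nor reported.

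A second reply is that the aim, design and endpoints compare measurements and do not test detection of dysfunction, and that the replacement sentence is conditional and sits in the ethics section. This also stands, and it is why narrowing the sentence is an acceptable remedy. But the condition is good correlation and agreement, with no requirement that these be shown at low movement.

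Third, a Bland-Altman plot already sets differences against size of movement. True, but the plan commits to no estimate of bias or limits at the low end.

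Fourth, deleting one line guarantees no low-movement participants. Recognised left-sided cases would add little to a right-sided primary comparison, and the neuromuscular exclusion would remain. All of this is correct and limits what the eligibility change can achieve.

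**Conclusion.** The mismatch is in the text: recognised dysfunction is excluded from every Study 1 group, while the conclusion is worded for patients with suspected dysfunction. Agreement at low movement may be poorly tested. How poorly cannot be calculated, because the documents give no count of recognised cases, no rate of unrecognised ones, no definition of low movement and no SD of paired differences. The table above rests on assumed rates and is illustrative only.

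The paired comparison remains valid for the people enrolled; the issue is how far it carries.

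Three further inferences should be resisted.

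- The Perspective statement that "The first study will identify the optimal research method" does not mention dysfunction and need not be reworded on this ground.
- The documents do not say that a low Study 2 measurement makes a patient a known case and so ineligible for Study 1; they define no threshold.
- A narrower range tends to lower the correlation with fluoroscopy. That works against a falsely good correlation and does not add to the risk described here.

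**What to change.** 1. In the Study 1 exclusion criteria, in the protocol and the layman's summary, apply the known-dysfunction item to the healthy group only. Keep the total at 100.
2. In Data analysis, Study 1, add bias and limits of agreement as a function of movement size, for example regression-based Bland-Altman limits, for M-mode and any other method measured in the same unit as fluoroscopy. State how many participants had low right-sided movement on fluoroscopy, using a definition that the sponsor fixes before analysis.
3. If the exclusion is kept, or few low-movement participants are enrolled, limit the statement in Ethical considerations, Study 1, and in its layman's counterpart, to people without known dysfunction. Do not conclude that fluoroscopy can be dropped when dysfunction is suspected.

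The cost is one eligibility line in an amendment, in two places, and a short addition to the analysis text. No extra participants or procedures are needed. The change permits low-movement participants but does not secure them, which is why item 3 is needed as a fallback. The SD of the differences may rise if agreement is worse at low movement. That would reduce power for the mean bias, but it is information the stated use requires.

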## STUDY 2:

Inclusion criteria:

- o Completed informed consent.
- One of the following:
  - Planned LVAD implantation / Heart transplant
  - Planned surgery for lung cancer/esophageal cancer. For lung cancer, the planned operation must be the removal of one or more lung lobes.

Exclusion criteria:

- Known diaphragm dysfunction
- o Neuromuscular disease
- Pleural effusion (over 1 cm)
- Pneumothorax

## RECRUITMENT

## STUDY 1:

## FAST GROUP:

Patients who are to be operated on in day surgery at Aarhus University Hospital. In the course of surgery (before or after, when patients are awake and capable), patients are informed about the project by a doctor associated with the trial. It is ensured that the information can be conveyed in an undisturbed single room. Participant information is provided. On the project day (a later date), if there is a desire for this, there will be the possibility of a follow-up interview with the possibility of the participation of co-chairs. The reflection time will thus be >1 day. Written consent is then secured. Patients have the option of withdrawing consent at any time without further requirements for a reason.

[figure not shown]
Day surgery Informed by doctor. Delivery of participant information

Project day Additional information if desired, with co-owners. Completing informed consent.

## HEART TRANSPLANT RECIPIENTS/LVAD GROUP:

This patient group is checked with frequent checks after the heart transplant/LVAD. In order to ensure a stable phase, all patients who have had a heart transplant and are checked at AUH after 6 months will be invited to participate in the present project. The patients will per letter to be informed by a doctor associated with the trial about participation. The patients are invited at the next scheduled outpatient visit (as part of the transplant/LVAD check-up) to hear more about the project. It is ensured that the information can be conveyed in an undisturbed single room, where oral information is given as well as written information is provided. On the project day (a later date), if there is a desire for this, there will be the possibility of a follow-up interview with the possibility of the participation of co-chairs. The reflection time will thus be >1 day. Written consent is then secured. Patients have the option of withdrawing consent at any time without further requirements for a reason.

Scheduled outpatient visit More info. Delivery of participant information

Project day Additional information if desired, with co-owners. Completing informed consent.

## PULMONARY GROUP:

Patients who visit the COPD clinic or the Center for Rare Lung Diseases are informed about the project by a doctor associated with the trial. It is ensured that the information can be conveyed in an undisturbed single room. Participant information is provided. On the project day (a later date), if there is a desire for this, there will be the possibility of a follow-up interview with the possibility of the participation of co-chairs. The reflection time will thus be >1 day. Written consent is then secured. Patients have the option of withdrawing consent at any time without further requirements for a reason.

Lung outpatient visit Informed by doctor. Delivery of participant information

Project day Additional information if desired, with co-owners. Completing informed consent.

## STUDY 2:

## PLANNED HEART TRANSPLANTATION:

Patients who are registered on the heart transplant list, etc. imminent heart transplant, will be informed about the project at the preliminary examination for this treatment or regular check-up prior to heart transplantation, which takes place in a private room. Both oral and written information is given here. After being put on the waiting list, patients will be informed and written consent will then be secured. Relatively close to this date, there will be the possibility of a follow-up interview with the possibility of the participation of co-chairs. The reflection time will thus be >1 day.

Registration for a heart transplant: Informed by doctor. Delivery of participant information

At least 2 days after the prescription: Additional information if desired, with co-owners. Completing informed consent.

## PLANNED LVAD:

Patients who have imminent treatment with an LVAD will be informed about the project during the preliminary examination for this treatment, which takes place in a private room. Both oral and written information is given here. The day before the operation, when the patients are all already admitted to optimize their cardiac condition, written consent is secured. On this day, there will be an opportunity for a follow-up interview with the possibility of the participation of co-chairs. The reflection time will thus be >1 day.

LVAD pre-study: Informed by doctor. Delivery of participant information

The day before LVAD surgery: Additional information if desired, with co-owners. Completing informed consent.

